7.1. Disposition of Participants and Withdrawals

Since this is a long-term study in a patient population that is elderly with multiple possible comorbidities, some participant withdrawal will occur. Efforts will be taken to obtain information on participants who are initially categorized as lost to follow-up. From the randomized population, the disposition of participants withdrawing from each treatment arm will be summarized and compared.

Version 1.0 | 28-Feb-2025 Page 24 of 56

Participant disposition will include tabulations of the number of overall participants who screen failed for blinded treatment period. The following will be summarized by randomized treatment group and overall:

- Number of participants who enrolled/randomized,
- Number and percentage of participants in each analysis set,
- Number and percentage of participants who completed the study, and
- Number and percentage of participants who discontinued from the study, including the reason for study discontinuation.

The percentage of participants will be based on the mITT analysis set. All disposition results will be presented in a data listing.

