4.3. Interim Analysis and Data Monitoring

No interim efficacy analyses or sample size re-estimations were planned to be conducted.

An external DSMB will be involved in the management of this study. The DSMB meeting will be held periodically for the duration of the study. The purpose of the DSMB is to review the progress of the study with special regard to safety and make recommendations to the Sponsor on how to handle any safety concerns that arise. Further details regarding the DSMB can be found in the DSMB charter which was finalized before the first meeting was scheduled.

Version 1.0 | 28-Feb-2025 Page 18 of 56

Statistical Analysis Plan, Sponsor: Cassava Sciences, Inc. Protocol Number: PTI-125-06 PCN Number: CASA215435

5. Analysis Populations

The following analysis sets were originally planned for this study:

- Intent-To-Treat (ITT) Analysis Set: The ITT analysis set includes all randomized participants.
- Intent-To-Treat mild (ITT-mild) Analysis Set: The ITT-mild analysis set includes all randomized participants who have a baseline MMSE of 21-27.
- Safety Analysis Set (SAF): The SAF analysis set includes all participants who received at least one dose of study treatment. All safety analyses will be completed in the SAF analysis set and participants will be included in the group based on the treatment received.
- **PK sub-study Analysis Set:** The PK sub-study analysis set includes all participants who sign the PK consent and/or re-consent form and have at least one non-missing post baseline PK assessment available.
- **Sub-study analysis sets:** Analysis sets for the Plasma, CSF, and imaging biomarkers will each be created as subsets of the ITT dataset that includes only those participants from the ITT analysis set who were in the relevant sub-studies.
- MRI sub-study Analysis Set: The MRI sub-study analysis set includes all participants who sign the MRI consent and/or re-consent form and have at least one non-missing post baseline MRI assessment available.

After the early termination, the following analysis sets were added:

- Modified intent-to-treat analysis set (mITT): The mITT analysis set is a subset of the ITT analysis set that includes all randomized participants with baseline P-tau181 ≥44 pg/ml or other evidence of amyloid pathology (e.g., Amyloid PET).

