If partial times occur, the convention is as follows: if the missing time occurs on the day of the first dose and both the hour and minute are missing then the time assigned is the time of the first dose, otherwise if both the hour and minute are missing and the date is not the date of first dose the time assigned is 12:00; if the date is the same as the date of the first dose and only hour is missing the hour assigned is 12 or the hour of first dose, whichever is later, and if the date is the same as the date of first dose and only the minute is missing the minute assigned is 30 or the minute of first dose, whichever is later. Otherwise, the hour assigned is 12 if the hour is missing and the date is not the same as the date of first dose and the minute assigned is 30 is the date is not the same as the date of first dose.

These conventions will be applied only to adverse event onset dates and times with the following precaution: if the missing date and time reflect the date and time of onset of an adverse event, the modified date and time will be constructed to match the first documented date/time post drug administration while preserving the order in which the AE was reported in the CRF.

[figure not shown]
7. Study Participants and Demographics

Participant disposition, demographics and other baseline characteristics, prior medications, and study drug exposure and compliance will be summarized by randomized treatment group and overall, using the ITT analysis set, unless otherwise specified below in each section.

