13.1. Demographic Data Summary Tables and Figures

Table 5: Demographic Data Summary Tables and Figures

Table Number	Population	Table Title/Summary
14.1.1	All Subjects	Subject Disposition (Includes All Early Terminations)
14.1.2.1.1	ITT	Demographics and Baseline Characteristics
14.1.2.1.2	ITT-mild	Demographics and Baseline Characteristics
14.1.2.1.3	mITT	Demographics and Baseline Characteristics
14.1.2.2	Safety	Demographics and Baseline Characteristics
14.1.2.3.1	ITT	Medical History
14.1.2.3.2	ITT-mild	Medical History
14.1.2.4.1.1	ITT	Prior Medications
14.1.2.4.1.2	ITT-mild	Prior Medications
14.1.3.1	Safety	Study Drug Exposure
14.1.3.2	Safety	Study Drug Compliance by Visit
14.1.4.1	ITT	Important Protocol Deviations
14.1.4.2	ITT-mild	Important Protocol Deviations

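### SAP 7.1 counts the disposition of all randomised participants but bases the percentages on mITT, a subset, so the table does not add up

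*SAP*

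**What the plan says.** The opening paragraph of SAP Section 7 sets the default for disposition and baseline summaries: "using the ITT analysis set, unless otherwise specified below in each section". Section 7.1 then describes who is tabulated: "From the randomized population, the disposition of participants withdrawing from each treatment arm will be summarized and compared". The rows to be shown by randomised arm and overall include "Number and percentage of participants in each analysis set", the number and percentage who completed, and "Number and percentage of participants who discontinued from the study, including the reason for study discontinuation". The section ends its description of the table with "The percentage of participants will be based on the mITT analysis set".

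Section 5 defines the two sets. For ITT: "The ITT analysis set includes all randomized participants". For mITT: "The mITT analysis set is a subset of the ITT analysis set that includes all randomized participants with baseline P-tau181" of at least 44 pg/ml, or other evidence of amyloid pathology. The mITT set was added after the early termination, and Section 2.2 expects it to be smaller than the full sample. In Section 13.1, Table 5 lists one disposition table, 14.1.1, with All Subjects as its population. No separate mITT disposition table is listed.

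**The concern.** A percentage needs a denominator that contains everyone in its numerator. Here the rows count people from the whole randomised population, while the stated denominator contains only those who meet the biomarker condition. Nothing in Section 7.1 restricts the counts to mITT, and no other section gives a different denominator for these rows.

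This is the table that shows how many participants completed, how many stopped and why, in a trial that ended early. Readers will use it, among other things, to judge how plausible the missing-at-random assumption is in each arm and to compare dropout with the 20% assumed at the design stage. That 20% applies to enrolled participants, so only an all-randomised rate can be set against it.

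**Working it through.** **Base for the illustration.** Section 7.1 contains no figure of its own, so I use the planned sample size in SAP Section 2.2. The inputs are a placebo change of 6.0, a 45% difference (0.45 × 6.0 = 2.7 points), SD 10.0, two-sided alpha 0.05 and 90% power. Then n = 2 × (1.960 + 1.282)² × (10/2.7)², which rounds up to 289 per arm, as stated. Dropout of 20% gives 289/0.80 = 361.25; the plan states about 361 per arm, and 3 × 361 = 1083. The base is reproduced.

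**Correct percentages at plan.** With 361 randomised per arm and 20% dropout, 72 discontinue and 289 complete. Over all randomised: ITT 361/361 = 100%; discontinued 72/361 = 19.9%; completed 289/361 = 80.1%. The last two sum to 100%.

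**Percentages under the rule as written.** Let m = mITT/ITT. The documents do not give m, so the range below is an assumption. The denominator is m × 361, rounded to a whole participant, and each entry is 100 × count / denominator.

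| Assumed m | mITT per arm | ITT row | Discontinued | Completed |
|---|---|---|---|---|
| 1.00 | 361 | 100.0% | 19.9% | 80.1% |
| 0.95 | 343 | 105.2% | 21.0% | 84.3% |
| 0.90 | 325 | 111.1% | 22.2% | 88.9% |
| 0.80 | 289 | 124.9% | 24.9% | 100.0% |
| 0.70 | 253 | 142.7% | 28.5% | 114.2% |
| 0.60 | 217 | 166.4% | 33.2% | 133.2% |

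Two results do not depend on the assumed range. The ITT row is 1/m, so it exceeds 100% for any m below 1. If every randomised participant is classed as completed or discontinued, those two rows also sum to 1/m. The Safety row exceeds 100% too if nearly all randomised participants were dosed. Small sub-study sets need not exceed 100%, but not all of their members need be in the denominator. At the planned dropout, completed alone passes 100% once m falls below 289/361 = 0.80.

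**The alternative reading.** Suppose both numerator and denominator are restricted to mITT. Completion and discontinuation rates are then correct for mITT. But randomised participants outside mITT disappear from the only disposition table, against the randomised-population wording of Section 7.1 and the All Subjects label in Table 5. The analysis-set row also fails, because ITT cut down to mITT is no longer ITT.

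**Between arms.** If m differs by arm, equal dropout prints as unequal. With 72/361 discontinued in both arms and m of 0.75 and 0.70, the table shows 72/271 = 26.6% and 72/253 = 28.5%.

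**The case against.** The case on the other side has weight on several points.

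- The Section 7 default allows a section to specify another set, and 7.1 does so. Departing from ITT is therefore permitted. The fault lies in the mismatch between the counts and the denominator inside 7.1.
- Basing percentages on a set can mean that both parts of the fraction come from it. A reader might infer from the text that the discontinuation rates by arm will simply be wrong. The documents do not establish that: with restricted numerators those rates would be valid for mITT, which is the set used for the co-primary analysis. What stands is that neither reading makes the whole table work.
- A reader might also infer a systematic distortion between arms. The documents do not support this. mITT membership depends on baseline status, so under 1:1:1 randomisation it differs between arms only by chance. At 361 per arm and an assumed m of 0.80, the standard error of the difference in m is √(2 × 0.80 × 0.20/361) ≈ 0.03. A shift of that size moves a printed 25% by about one point (20/0.80 = 25.0 against 20/0.83 = 24.1).
- The mITT share may be close to 1. Protocol inclusion criterion 5 already required evidence of AD pathophysiology, and the plasma cutoff for entry is in a laboratory manual outside these documents. Section 2.2 expects a smaller sample but gives no size. The lower values of m above are illustrations only.
- The raw counts by arm are in the same table, and Table 8 plans participant listings of disposition and analysis populations, so a careful reader can recompute. Departures from missing at random have their own copy-reference sensitivity analysis in Section 8.1.1, so the disposition table is not the only evidence on that question.

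**Conclusion.** The rule in Section 7.1 does not work as written. The ITT row and the completed-plus-discontinued total exceed 100% once any randomised participant is outside mITT, and no other section repairs this. How far the printed rates are off depends on m: for assumed m from 0.95 to 0.60, a true 20% discontinuation rate prints as 21% to 33%. The 20% is the planning value, and the early stop may well have raised the actual figure; the same factor 1/m applies to whatever rate occurred. These figures assume all-randomised numerators, which is the more natural reading of the text but not the only possible one.

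This is a reporting error. It changes no estimate, test or error rate for efficacy, and the counts needed to correct it remain available.

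**What to change.** Replace the last sentence on the disposition table in Section 7.1 with one saying that percentages use all randomised participants (the ITT set) as denominator, by randomised arm and overall. The mITT row of the analysis-set counts then shows directly what share of each arm enters the primary analysis.

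Add a second block to Table 14.1.1, or a companion table, giving completion and discontinuation by reason within mITT, with numerator and denominator both restricted to that set. This keeps the dropout information that matches the co-primary analysis population without losing the all-randomised picture.

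The cost is one sentence of SAP text and one revised table shell. No new data and no change to any efficacy analysis are needed.

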7.2. Protocol Violations and Deviations

The severity (important/non-important) will be classified using the following definitions as per Premier Research standard operating procedures (SOPs). A protocol deviation is any noncompliance with the clinical trial protocol or International Council for Harmonization of Technical Requirements for Pharmaceuticals for Human Use (ICH) E6 (R2) Good Clinical Practice (GCP) requirements.

Protocol deviations will be tracked, recorded, and reviewed prior to database lock, following the Protocol Deviation Guidance Plan for this study.

[figure not shown]
Potentially important deviations will be reviewed by the Sponsor and Premier to determine the final classification. Protocol deviations which are deemed to be "Important" and "Non-Evaluable" (i.e., a deviation that has a potential impact on the efficacy analysis), will be classified into a separate category.

The protocol deviation categories will be:

- Inclusion Criteria
- Exclusion Criteria
- Study Drug
- Assessment Safety
- Assessment Efficacy
- Lab/Endpoint Data
- Visit Window
- Informed Consent
- Prohibited Concomitant Medication
- Overdose/Misuse
- Other

The number and proportion of participants with important protocol violations/deviations will be tabulated by category/type and treatment group in the safety analysis set. These protocol violations/deviations will also be presented in a participant listing by randomized treatment.

Version 1.0 | 28-Feb-2025 Page 25 of 56

7.3. Demographics and Other Baseline Characteristics

All participant demographics and other baseline characteristics will be summarized by randomized treatment group using the ITT analysis set. Demographic and other baseline characteristics will also be summarized for the safety analysis set if it is different from the ITT analysis set.

Demographic and baseline characteristics [age, sex (including child-bearing potential for women), methods of contraception, race, ethnicity, weight, height, body mass index (BMI), and education level] will be summarized using the descriptive statistics. Height and weight will be calculated at screening and then the BMI will be calculated at screening.

Additionally, baseline characteristics including AD family history, Covid-19 infection and vaccination history results, and Apolipoprotein E (ApoE) genotyping will be summarized.

The number and percent of participants reporting medical history, grouped by MedDRA system organ class and preferred term, will be tabulated by randomized treatment group. All medical history data will be presented in a data listing.

Prior medications will be summarized descriptively by treatment group using the number and percentage of participants by Anatomical Therapeutic Chemical class (ATC level 2) and preferred term (ATC level 4). All "Cognitive enhancers" defined by verbatim terms: donepezil (Aricept, Adlarity), galantamine (Razadyne, Reminyl), rivastigmine (Exelon) and memantine (Namenda, Ebixa, Nemdatine) will be summarized separately. All prior medication data will be listed. The cognitive enhancers will be flagged in the prior medication listing.

For the continuous variables, the number of non-missing values and the mean, standard deviation, minimum, median, and maximum will be tabulated.

For the categorical variables, the count and percentage of each value will be tabulated.

7.4. Exposure and Compliance

Study drug exposure and compliance data will be collected in the case report form (CRF).

[figure not shown]
Study drug exposure data will be summarized as treatment duration (days), study drug exposure (days), and average daily dose (mg/day) by treatment received and overall.

Study drug compliance data will be summarized as total number of planned doses (tablets), total number of doses (tablets) taken, and compliance (%) by treatment received and visit.

Compliance will be summarized as a continuous outcome using mean, SD, median, min, and max, and as a categorical variable. For the categorical analysis, a participant will be considered compliant if the amount of medication taken is within the range of 75% - 125% of the amount of medication planned to be taken.

All study drug administration, accountability and exposure data will be listed.

Version 1.0 | 28-Feb-2025 Page 26 of 56

8. Efficacy Analysis

8.1. Co-Primary Efficacy Analysis

Visit wise mean changes from baseline will be analyzed in the mITT analysis set using a restricted maximum likelihood (REML)-based repeated measures approach (MMRM). The MMRM analysis assumes a missing at random (MAR) missing-data mechanism, meaning that drop out is related to observed outcomes of the dependent variable and covariates, but not to the unobserved outcomes. The analysis will include the categorical, fixed effects of treatment group (3 levels), visit (7 levels), and pooled site, along with the continuous, fixed covariates of baseline value of the endpoint being analyzed (baseline), baseline MMSE score, and the interactions of treatment group, baseline, and baseline MMSE with visit. An unstructured (co)variance structure will be used to model the within-participant errors. If this analysis fails to converge, the following structures will be tested in this order, with the first structure yielding convergence to be used as the appropriate structure for that variable: heterogeneous Toeplitz, heterogeneous compound symmetric, and compound symmetric. If one of the structures other than unstructured is used, variance of the Maximum Likelihood Estimator (MLE) will be based on the Sandwich Estimator (empirical option in PROC MIXED statement). If none of the structures yield convergence, site will be removed from the model and the sequence of covariance structures will be refit as described above. The Kenward-Roger approximation will be used to estimate denominator degrees of freedom.

Significance tests for the between-treatment group differences will use a two-sided 0.05 level, with the co-primary analyses using the mITT analysis set.

8.1.1. Sensitivity Analyses of the Primary Efficacy Endpoint

The co-primary analyses will also be applied to the ITT, cITT, and ITT-mild analysis sets.

In addition, a missing not at random (MNAR)-based copy reference approach will be used as a sensitivity analysis to assess robustness of inferences on the co-primary analyses, (mITT analysis set) to departures from MAR. Mean changes from baseline in the co-primary endpoints will be analyzed based on data observed while the participants remain on study as well as data imputed using multiple imputation for time points at which no value is observed.

[figure not shown]
Imputation of values in the reference (placebo) arm will assume MAR. Imputation of values in the active arm will be based on the imputation model for the placebo group, thereby imputing placebolike values for drug group dropouts. This approach assumes any benefit from the active treatment diminishes over time in accordance with the correlations between repeated measurements.

Intermittent (non-monotone) missing data will be imputed first based on MCMC. An example code fragment is included below. YOBS1-7 are the seven postbaseline values of the endpoint being imputed.

```
PROC MI DATA = XXX OUT = YYY_MIOUT NIMPUTE=200 SEED=123;
  BY TRT;
  MCMC IMPUTE = MONOTONE;
  VAR BASELINE MMSE_BASELINE YOBS1 YOBS2 YOBS3 YOBS4 YOBS5 YONS6 YOBS7;
RUN;
```

The remaining monotone missing data for all participants who discontinue study prematurely will be imputed using a sequential regression multiple imputation model based on data from the

Version 1.0 | 28-Feb-2025 Page 27 of 56

reference arm (placebo, denoted as trt 1 in the code below) only. Missing values in the placebo and two active arms will be imputed from the imputation model developed from the placebo arm. No rounding or range restrictions will be applied to imputed continuous values.

Example code to implement this analysis is listed below.

```
PROC MI DATA=YYY_MIOUT SEED=1214 OUT=YYY_MIOUT2 round=1 NIMPUTE=200;
CLASS TRT;
MONOTONE METHOD=REG;
VAR BASELINE MMSE BASELINE YOBS1 YOBS2 YOBS3 YOBS4 YOBS5;
MNAR MODEL (Y1 / modelobs=(trt'1'));
MNAR MODEL (Y2 / modelobs=(trt'1'));
MNAR MODEL (Y3 / modelobs=(trt'1'));
MNAR MODEL (Y4 / modelobs=(trt'1'));
MNAR MODEL (Y5 / modelobs=(trt'1'));
MNAR MODEL (Y6 / modelobs=(trt'1'));
MNAR MODEL (Y7 / modelobs=(trt'1'));
MNAR MODEL (Y7 / modelobs=(trt'1'));
Run;
```

The primary MMRM model will be applied to the multiply imputed data sets with results combined using Rubin's rules as implemented in PROC MI Analyze.

Another sensitivity analysis will employ a hypothetical strategy rather than the treatment policy strategy for changes in concomitant medications that are known to have a cognitive enhancing effect. This analysis will be identical to the primary analysis except that data will be censored after a participant has a post-baseline change in dose or a post-baseline initiation of a cognitive enhancing treatment. By deleting the post-change in concomitant medication data, the MMRM analysis will estimate what would be expected if the participants had not added or initiated cognitive enhancing medication.

To assess sensitivity of inferences to handling of the intercurrent event of death, the following approach will be used. Missing data resulting from patient death will be imputed using the worst observed result at each respective visit. The primary analysis as described above will be applied to this data set.

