#### 9. EARLY DISCONTINUATION

Subjects may choose to discontinue Study Drug or study participation at any time, for any reason, and without prejudice. Moreover, a subject may be withdrawn at any time at the discretion of the Investigator or Sponsor for safety, behavioral or administrative reasons. Discontinued subjects should be followed according to medical practice standards, and the outcome documented. Follow-up is required if the subject is discontinued due to an adverse event (AE). Any comments (spontaneous or elicited) or complaints made by the subject and the reason for termination and the date of stopping the drug must be recorded in the Case Report Form (CRF) and source documents.

The following must be completed and documented in the source documents and CRFs for all subjects who discontinue the study early:

- The reason for early study discontinuation. If the subject is withdrawn for more than one reason, each reason should be documented in the source documents and the most clinically relevant reason should be entered on the CRF.
- Vital signs (blood pressure, temperature and pulse), brief physical and neurologic examination, weight, clinical laboratory tests, 12-lead resting ECG (5 min supine), use of concomitant medications and adverse events should be obtained at discharge prior to release.
- Blood draw for plasma biomarkers
- ADAS-Cog12, MMSE, CDR, ADCS-ADL, NPI, ZBI and C-SSRS (as detailed in Section 7.1.7 Early Termination Visit), if not performed within the last 30 days.

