3.2. Estimands

The primary estimand for the primary efficacy endpoints is defined as follows:

Population	The original population was specified as: Participants with mild-to-moderate AD dementia who meet the study's inclusion and exclusion criteria. The
	population of interest was changed after early termination, but while still

Version 1.0 | 28-Feb-2025 Page 15 of 56

	blinded, to: Participants with mild-to-moderate AD dementia who meet the study's inclusion and exclusion criteria, and who have baseline P-tau181 ≥ 44 pg/ml or other evidence of amyloid pathology.
Treatments	Simufilam 100 mg twice daily or placebo (50mg twice daily is secondary).
Endpoints	ADAS-Cog12 (range $0-80$, higher score indicates greater impairment) and ADCS-ADL (range $0-78$, lower score indicates greater impairment).
Summary Measure	Difference between treatments in least squares (LS) mean change from baseline to Week 76.
Intercurrent Events	All deviations from the intended dosing regimens and use of concomitant medication will be handled using a treatment policy strategy. Early study discontinuation will be consistently accounted for using a hypothetical strategy to estimate what would have been observed if the participant had not discontinued.

The estimands for the multiplicity controlled secondary efficacy endpoint(s) are similar to the co-primary estimands. Each secondary estimand has the following components:

Population	The original population was specified as: Participants with mild-to-moderate AD dementia who meet the study's inclusion and exclusion criteria. The population of interest was changed after the early termination, but while still blinded, to: Participants with mild-to-moderate AD dementia who meet the study's inclusion and exclusion criteria, and who have baseline P-tau181 ≥ 44 pg/ml or other evidence of amyloid pathology.
Treatments	Simufilam 100 mg twice daily or placebo (50 mg twice daily is secondary)
Endpoints	iADRS, NPI-10, MMSE, CDR-SB, ZBI
Summary Measure	Difference between treatments in LS mean change from baseline to week 76
Intercurrent Events	All deviations from the intended dosing regimens and use of concomitant events medications will be handled using a treatment policy strategy. Early study discontinuation will be consistently accounted for using a hypothetical strategy to estimate what would have been observed if the participant had not discontinued.

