6.1.4. Handling of Dropouts or Missing Data

[figure not shown]
The original plan was that every attempt would be made to ensure participants remain in the study to completion and all data is collected as scheduled, the occurrence of missing data cannot be completely prevented. The early study termination creates more missing data than originally anticipated. However, the administrative censoring is independent of the treatments and outcomes in this study and is therefore considered missing completely at random. Therefore, the missing data from early stopping will not bias the MMRM results.

An incomplete start or stop date of an AE or a medication will be imputed as described in section 6.1.8.

Any participant who withdraws from the study will be considered to have missing data at all subsequent visits. The primary analytic approach for efficacy assumes missing at random (MAR) to estimate what would have been observed if the participant had not discontinued. A reference-based multiple imputation sensitivity analysis (copy reference) will be employed in which missing not at random is assumed such that after discontinuation, drug-treated participants will have placebo-like values imputed for their missing data.

If up to two individual items of the total 12 items for the ADAS-Cog12 (maximum score = 80) are missing for non-cognitive reasons, the total score will be imputed by multiplying the observed score (i.e. the score for the non-missing items) by a factor that includes the maximum scores for the missing item(s) as follows:

Version 1.0 | 28-Feb-2025 Page 20 of 56

Imputed score = Observed score * (80/[80-maximum score for missing items]).

As an example, if the first item "Word Recall" (maximum score = 10) and the second item "Commands" (maximum score = 5) are missing, the observed score will be multiplied by the factor 80/(80-[10+5]) or 80/65 or 1.23. The imputed score will be rounded to the nearest integer. ADASCog12 tests with more than two missing items will be considered missing scores.

Missing items on other assessments will not be imputed; such scores will be considered missing.

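### The copy-reference sensitivity analysis gives placebo-like values to active-arm data lost to the sponsor's termination, and its example code does not match its text

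*SAP*

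**What the plan says.** SAP 6.1.4 accepts that the early stop leaves more missing data than planned, but regards it as harmless to the MMRM: "the administrative censoring is independent of the treatments and outcomes in this study and is therefore considered missing completely at random". The same section introduces the copy-reference analysis, under which "after discontinuation, drug-treated participants will have placebo-like values imputed for their missing data".

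SAP 8.1.1 gives the detail. The analysis is run in the mITT set to examine departures from MAR. Intermittent gaps are filled first by MCMC. Then: "The remaining monotone missing data for all participants who discontinue study prematurely will be imputed using a sequential regression multiple imputation model". That model is built from the placebo arm and used for missing values in all three arms. The text covers every time point without an observed value. Neither text nor code carries a flag for the reason or date of discontinuation.

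The estimand in SAP 3.2 reads: "Early study discontinuation will be consistently accounted for using a hypothetical strategy", meaning that the target is what would have been seen had the participant stayed in. The reason for leaving is recorded: Protocol section 9 requires "The reason for early study discontinuation", and SAP 7.1 tabulates "Number and percentage of participants who discontinued from the study, including the reason for study discontinuation".

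SAP 8.1.1 also supplies two blocks of example code. The first contains the line "VAR BASELINE MMSE_BASELINE YOBS1 YOBS2 YOBS3 YOBS4 YOBS5 YONS6 YOBS7".

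**The concern.** Copy reference is the only dropout analysis that the SAP labels MNAR. Its purpose is to show whether the co-primary result survives if people who left did worse than MAR predicts. For ordinary dropouts, a move toward placebo is a deliberate pessimistic assumption. For participants cut off by the sponsor there is nothing to be pessimistic about, because the SAP itself says the loss is unrelated to treatment and outcome. Giving them placebo-like values changes the target of estimation because of a sponsor decision.

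If the effect then shrinks, the result alone will not show whether the cause is fragility to informative dropout or the administrative stop. Placebo participants are not distorted, since the placebo model is simply MAR for them.

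The code is a second problem. It is the only operational specification of this analysis, and it does not implement the text beside it.

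**Working it through.** **Planned effect.** SAP 2.2 assumes a placebo change of 6.0, a 45% difference and an SD of 10.0, so the effect is 0.45 × 6.0 = 2.7 points. The stated size reproduces: 2 × (1.960 + 1.282)² × 10² / 2.7² = 288.3, that is 289 per group. Then 289 / 0.8 = 361.25, against 361 stated.

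**Scope, read side by side.** SAP 6.1.4 classes termination losses as MCAR. SAP 8.1.1 applies the placebo model to all premature discontinuations, to all unobserved time points and to both active arms. The second rule therefore covers the data described by the first.

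**Size.** The SAP gives neither the share of active-arm Week 76 values lost to termination (*f*), nor the stop timing, nor the covariance. All three are assumed here, as is a linear build-up of the effect, δ(week) = 2.7 × week / 76, at Weeks 4, 16, 28, 40, 52, 64 and 76. Under copy reference, a participant last seen at visit *k* keeps this share of the Week 76 effect:

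kept(*k*) = Σ(7, 1..*k*) · Σ(1..*k*, 1..*k*)⁻¹ · δ(1..*k*) / δ(7)

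and overall, retained = 1 − *f* × (1 − mean kept).

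| Assumed covariance | kept for k = 1 to 6 | mean |
|---|---|---|
| A: AR(1), 0.8 between adjacent visits | 0.01, 0.07, 0.15, 0.27, 0.44, 0.67 | 0.27 |
| B: compound symmetric, 0.6 | 0.03, 0.10, 0.17, 0.25, 0.33, 0.40 | 0.21 |
| C: random slope 75% of Week 76 variance, shared baseline error 12.5%, visit error 12.5% | 0.03, 0.20, 0.44, 0.64, 0.78, 0.87 | 0.49 |

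Worked case, B with *k* = 6: each earlier visit has weight 0.6 / (1 + 5 × 0.6) = 0.15. The weeks sum to 204, so kept = 0.15 × 204 / 76 = 0.40. With stops spread evenly over visits and *f* = 30%: 1 − 0.3 × (1 − 0.213) = 0.764, and 0.764 × 2.7 = 2.06 points.

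| *f* | Even stops, A / B / C | All last seen at Week 64, A / B / C |
|---|---|---|
| 20% | 85 / 84 / 90% | 93 / 88 / 97% |
| 30% | 78 / 76 / 85% | 90 / 82 / 96% |
| 50% | 63 / 61 / 75% | 84 / 70 / 93% |

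In points, the range is 2.06 to 2.59 at 30% and 1.64 to 2.52 at 50%.

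A simulation gave the same direction. It used 361 per arm, 400 runs, AR correlation 0.8 with SD growing over time, and even stops. Copy reference gave 2.21 points at 30% lost and 1.83 at 50%. Imputing the same values within arm gave 2.68 to 2.78 over losses of 10% to 50%.

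**Code against text.**
- The text defines seven post-baseline values. The VAR list in the second step stops at YOBS5 (Week 52), so Weeks 64 and 76 are absent and the co-primary time point would not be imputed.
- The MNAR statements name Y1 to Y7, not YOBS1 to YOBS7, and Y7 appears twice.
- The first step has YONS6 where YOBS6 is meant.
- The text rules out rounding, while the code sets round=1. The numerical effect is negligible: variance 1/12 against 10² = 100, about 0.08%.
- The second step asks for 200 imputations of a file that already stacks 200, with no BY _IMPUTATION_. If the stack were analysed as one data set, standard errors could be understated by up to √200, about 14-fold. This does not fit the Rubin's-rules combination that the text describes.

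**The case against.** The strongest reply is that the SAP never says outright that terminated participants receive placebo-like values. SAP 6.1.4 discusses the stop and participant withdrawals in separate paragraphs, and SAP 8.1.1 speaks at one point of dropouts in the drug group, which could mean ordinary withdrawals only. That reading conflicts with the unrestricted wording elsewhere in 8.1.1. If it was intended, the values lost to termination have no imputation rule in this analysis, so the SAP needs a sentence either way.

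It is also fair that this analysis has no place in the testing sequence, that the bias is toward no effect, and that no false claim of efficacy can follow from its scope. The disposition table and the fixed stop date would let a reader see roughly how much missingness came from the stop, and the split could be made afterwards. But it would then be unplanned. The cITT analysis does not fill the gap, because it is an MMRM on the ITT set and does not use copy reference.

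Two practical points stand. Protocol section 9 puts only the most clinically relevant reason on the CRF, so a participant already failing near the stop date could be coded as terminated. And the code is labelled as an example beside correct text, so the naming slips would be caught on programming; the truncated VAR list and the missing BY statement are the substantive faults.

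**Conclusion.** The concern holds and should be fixed before the analysis is run. As written, the copy-reference rule covers active-arm values that the SAP itself calls MCAR, so the check mixes an administrative stop with possible informative dropout. The direction is certain given a true benefit that builds over time: toward no effect. The size is not known. The retained shares of 76% to 96% at 30% lost, 84% to 97% at 20% and 61% to 93% at 50% rest on assumed loss, timing, covariance and linear build-up. With few or late stops the effect is small. The primary MMRM is unaffected. The code faults are plain from the text and need no assumption.

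**What to change.** State in SAP 8.1.1 that values missing because of the termination are imputed under MAR within the participant's own arm, and that copy reference applies only to discontinuations for other reasons. Derive the flag from the recorded discontinuation reason, cross-checked against the 25 November 2024 date, and confirm it at the blinded data review already planned in SAP section 5. In practice this takes one MAR run by treatment and one MNAR run, keeping for each participant the run that matches the flag.

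Correct the code:
- First step: YONS6 becomes YOBS6.
- Second step: add BY _IMPUTATION_ with NIMPUTE=1 and remove round=1.
- List BASELINE, MMSE_BASELINE and YOBS1 to YOBS7 in VAR.
- Use the same variable names in the MNAR MODEL statements, each once.

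The cost is SAP wording, a few lines of code, one flag and one extra imputation run. No new data should be needed, because the reason for discontinuation is already collected. The primary analysis does not change.
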